2. TYPE OF PLANNED ANALYSIS

2.1. Interim Analyses

2.1.1. Data Monitoring Committee Analysis

One external multidisciplinary Data Monitoring Committee (DMC) analysis was conducted after all subjects have completed their Week 16 visit or prematurely discontinued from study drug, all outstanding data queries had been resolved or adjudicated as unresolvable, and the data had been cleaned and finalized for the analysis. No formal stopping rules was used by the DMC for safety outcomes. Rather, a clinical assessment was made to determine if the nature, frequency, and severity of AEs associated with a study treatment warrant the early termination of the study in the best interest of the subjects. No alpha penalty will be applied for the primary analysis of the primary efficacy endpoint given that the study is not adequately powered for a formal efficacy evaluation. The purpose of the interim analysis was to provide the DMC with a statistical report for review. More details are documented in the DMC charter.

2.1.2. Week 28 Interim Analysis

The Week 28 interim analysis was conducted after all subjects have completed the Week 28 visit or have prematurely discontinued the study drug, outstanding data queries had been resolved or adjudicated as unresolvable, and the data had been cleaned and finalized for the analysis. The analysis was used to support the LEN regulatory filing for the indication in the heavily treatment experienced PWH.

2.1.3. Week 80 Interim Analysis

The Week 80 analysis will be conducted after all subjects either complete their Week 80 visit or prematurely discontinue from the study drug, outstanding data queries had been resolved or adjudicated as unresolvable, and the data had been cleaned and finalized for the analysis.

2.2. Primary Analysis

The Week 54 interim analysis is a planned primary analysis and will be conducted after all subjects have completed Week 54 visit or have prematurely discontinued the study drug, outstanding data queries have been resolved or adjudicated as unresolvable, and the data have been cleaned and finalized for the analysis.

This SAP describes the analysis plan for the Week 54 interim analysis, the primary analysis of this study.

2.3. Final Analysis

The final analysis will be performed after all subjects have completed the study or have prematurely discontinued the study drug, outstanding data queries have been resolved or adjudicated as unresolvable, and the data have been cleaned and finalized.

3. GENERAL CONSIDERATIONS FOR DATA ANALYSES

Analysis results will be presented using descriptive statistics. For categorical variables, the number and percentage of subjects in each category will be presented; for continuous variables, the number of subjects (n), mean, standard deviation (SD) or standard error (SE), median, first quartile (Q1), third quartile (Q3), minimum, and maximum will be presented.

All statistical tests will be 2-sided and performed at the 5% significance level for descriptive purpose unless otherwise specified.

By-subject listings will be presented for all subjects in the All Randomized Analysis Set and sorted by subject identification (ID) number, visit date, and time (if applicable). Data collected on log forms, such as AEs, will be presented in chronological order within the subject. The treatment group to which subjects were randomized will be used in the listings. Age, sex at birth, race, and ethnicity will be included in the listings, as space permits.

3.1. Analysis Sets

Analysis sets define the subjects to be included in an analysis. Analysis sets and their definitions are provided in this section. The analysis set will be identified and included as a subtitle of each table, figure, and listing.

For each analysis set, the number and percentage of subjects eligible for inclusion will be summarized by treatment group.

A listing of reasons for exclusion from analysis sets will be provided by subject.

3.1.1. All Randomized Analysis Set

All Randomized Analysis Set includes all subjects who were randomized in the study.

This is the primary analysis set for by-subject listings.

3.1.2. Full Analysis Set

The Full Analysis Set (FAS) includes all randomized subjects who were randomized and received at least 1 dose of study drug. This is the primary analysis set for efficacy analyses.

3.1.3. Per-Protocol Analysis Set

The Per-Protocol (PP) Analysis Set is defined for the primary efficacy analysis. This analysis set includes all subjects in the FAS excluding subjects meeting any of the following criteria:

- Subjects who do not have on-treatment HIV-1 RNA in the Week 54 analysis window, except when missing is due to discontinuation of study drug for lack of efficacy. (Note: lack of efficacy is defined as having the check-box for Lack of Efficacy marked as the reason for premature study drug discontinuation on the study drug completion eCRF page.)
- Subjects who meet the exclusion criterion that was known hypersensitivity to the study drug(s), the metabolites, or formulation excipient.
- Subjects who meet the exclusion criterion for receiving treatment within 3 months prior to screening, or anticipated treatment during the study period with immunosuppressant therapies, hydroxyurea, foscarnet, radiation, or cytotoxic chemotherapeutic agents that listed in Table 5-3 in protocol Section 5.4.
- Nonadherence to once daily (QD) study drug(s): subjects with adherence rate for active once daily study drug(s) up to the Week 54 Visit below the 2.5th percentile

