6.6. Criteria for Discontinuation of Study Treatment

Study medication may be discontinued in the following instances:

- Intercurrent illness that would, in the judgment of the investigator, affect assessments of clinical status to a significant degree. Following resolution of intercurrent illness, the participant may resume study dosing at the discretion of the investigator.
- Unacceptable toxicity, or toxicity that, in the judgment of the investigator, compromises the ability to continue study-specific procedures or is considered to not be in the participant's best interest
- Lack of efficacy
- Participant request to discontinue for any reason
- Participant noncompliance
- Pregnancy during the study; refer to [Appendix 4](#).
- Discontinuation of the study at the request of Gilead, a regulatory agency or an institutional review board (IRB) or independent ethics committee (IEC)

- Participants in Treatment Groups 1 and 2 will need to have HIV-1 RNA results < 50 copies/mL at Weeks 16 and 22 to initiate treatment with a two-agent regimen at Week 28; those with values \geq 50 copies/mL will discontinue the study drug at or prior to Week 28. If data are missing at either Weeks 16 or 22 the participants discontinuation should be discussed with the medical monitor.

CCI

[REDACTED]

[REDACTED]

[REDACTED]

[REDACTED]

[REDACTED]

[REDACTED]

[REDACTED]

[REDACTED]

[REDACTED]

[REDACTED]

[REDACTED]

[REDACTED]

CCI

[REDACTED]

[REDACTED]

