6.1.1. US FDA-defined Snapshot Algorithm

The analysis window at Week 54 is defined as from Study Day 323 to Study Day 413, inclusive. All HIV-1 RNA data collected on-treatment (ie, data collected up to 1 day after the last dose date) will be used in the US FDA-defined snapshot algorithm. Virologic outcome will be defined as the following categories:

- HIV-1 RNA < 50 copies/mL: this includes subjects who have the last available on-treatment HIV-1 RNA < 50 copies/mL in the Week 54 analysis window
- HIV-1 RNA \geq 50 copies/mL: this includes subjects
 - Who have the last available on-treatment HIV-1 RNA \geq 50 copies/mL in the Week 54 analysis window, or
 - Who do not have on-treatment HIV-1 RNA data in the Week 54 analysis window and
 - Who discontinue study drug prior to or in the Week 54 analysis window due to lack of efficacy, or
 - Who discontinue study drug prior to or in the Week 54 analysis window due to reasons other than AE, death, or lack of efficacy and have the last available on-treatment HIV-1 RNA \geq 50 copies/mL
- No Virologic Data in the Week 54 analysis window: this includes subjects who do not have on-treatment HIV-1 RNA data in the Week 54 analysis window because of the following:
 - Discontinuation of study drug prior to or in the Week 54 analysis window due to AE or death (regardless of whether the last available on-treatment HIV-1 RNA < 50 copies/mL or not) or,
 - Discontinuation of study drug prior to or in the Week 54 analysis window due to reasons other than AE, death, or lack of efficacy and the last available on-treatment HIV-1 RNA < 50 copies/mL or,
 - Missing data during the window but on study drug.

The flowchart of the US FDA-defined snapshot algorithm is provided in Section 12 ([Appendix 2](#)).

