6.1.3. Secondary Analysis for the Primary Efficacy Endpoint

A secondary analysis based on the Week 54 PP analysis set will also be performed to evaluate the robustness of the primary analysis of the primary endpoint. Subjects excluded from the Week 54 PP analysis set will be determined before database lock.

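### The first Per-Protocol exclusion drops participants without Week 54 data whom the snapshot counts as HIV-1 RNA ≥ 50, because its exception rests on a check-box and not on the RNA value

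*SAP*

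**What the plan says.** SAP 3.1.3 builds the PP set from the Full Analysis Set (FAS). Its first exclusion covers anyone lacking an on-treatment RNA result during the Week 54 window, "except when missing is due to discontinuation of study drug for lack of efficacy". A note adds that "lack of efficacy is defined as having the check-box for Lack of Efficacy marked as the reason for premature study drug discontinuation". No RNA criterion enters the exception.

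SAP 6.1.1 gives three routes to HIV-1 RNA ≥ 50 copies/mL at Week 54:

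- (a) participants "who have the last available on-treatment HIV-1 RNA" at or above 50 in the window (Study Days 323 to 413);
- (b) no on-treatment window data, and in the SAP's words: "Who discontinue study drug prior to or in the Week 54 analysis window due to lack of efficacy, or" the next route;
- (c) no on-treatment window data, and drug stopped "due to reasons other than AE, death, or lack of efficacy and have the last available on-treatment HIV-1 RNA" at or above 50.

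SAP 6.1.3 runs the PP analysis "to evaluate the robustness of the primary analysis of the primary endpoint". Protocol 6.6 adds a stopping rule for Groups 1 and 2 only: participants with HIV-1 RNA ≥ 50 at Week 16 or 22 "will discontinue the study drug at or prior to Week 28". Protocol 6.3.3 ties this to confirmed values.

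**The concern.** A route (c) participant is a failure in the primary analysis and is missing from the analysis that checks it. In the snapshot, a participant without window data whose last value is ≥ 50 is a failure whether the site records lack of efficacy or, say, investigator's discretion. In the PP set that same choice decides between counting as a failure and not counting at all.

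The Week 16/22 rule gives a concrete way for this to happen. It acts by Week 28 (Day 196), well before the Week 54 window opens on Day 323. Protocol 6.6 lists it separately from lack of efficacy, noncompliance and participant request, so a site could record such a stop under another heading. At stake is whether a PP rate above the FAS rate can be read as reassurance, when part of the gain may come from deleting virologic failures.

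**Working it through.** **1. Match each snapshot category to the first PP criterion.**

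| Snapshot category at Week 54 | On-treatment window RNA? | First PP criterion |
|---|---|---|
| < 50 | Yes | Kept |
| ≥ 50, route (a) | Yes | Kept, whatever box is ticked |
| ≥ 50, route (b) | No | Kept, by the exception |
| ≥ 50, route (c) | No | **Dropped** |
| No virologic data | No | Dropped |

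Everyone dropped is a snapshot non-success. With x successes among n participants and d dropped, the rate goes from x/n to x/(n − d), which cannot be lower.

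**2. Reproduce the plan's figures.** Power (SAP 1.3; 90.9% in both groups, margin 0.12, 50 vs 25): SE = √[0.909 × 0.091 × (1/50 + 1/25)] = 0.0704, and Φ(0.12/0.0704 − 1.96) = 39.9%, against 39% stated. This figure is not in dispute; it shows how little information each comparison carries. Week 54 snapshot success (Protocol 1.2.2.8): 47/52 = 90.4%, 45/53 = 84.9%, 44/52 = 84.6% and 23/25 = 92.0% in Groups 1 to 4.

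**3. Size in the subcutaneous groups.** Pooled FAS: (47 + 45)/(52 + 53) = 92/105 = 87.6%, so 13 non-successes. Assume that the 3 recorded lack-of-efficacy stops came before Week 54 and are kept, and that the other 10 non-successes have no window data. The current PP rate, before the other PP criteria, is 92/95 = 96.8%. If c of the 10 are route (c) and are put back as failures, it is 92/(95 + c):

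| c | 0 | 1 | 3 | 6 | 7 |
|---|---|---|---|---|---|
| PP rate | 96.8% | 95.8% | 93.9% | 91.1% | 90.2% |

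The value 7 is the ceiling if the 3 AE stops are among the 10, since AE stops cannot be route (c). If none of them is, the ceiling is 10 (92/105 = 87.6%).

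**4. Bound on rule-stopped cases.** Someone stopped under the Week 16/22 rule by Week 28 with a last on-treatment value ≥ 50 is a non-success at both Week 28 and Week 54. Protocol 1.2.2.8 gives:

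- Group 1: 52 − 49 = 3 non-successes at Week 28. Of the 47 Week 54 successes, 46 were suppressed at Week 28, so 1 of the 3 succeeded later. That leaves 2.
- Group 2: 53 − 49 = 4 non-successes at Week 28. All 45 Week 54 successes were suppressed at Week 28. That leaves 4.

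The total is at most 6 of 105, for any reason, including AE and correctly coded lack of efficacy.

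**5. Treatment difference.** Group 2 against B/F/TAF, with d non-successes dropped from each arm:

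| Dropped, Group 2 / B/F/TAF | Rates | Difference (points) |
|---|---|---|
| 0 / 0 | 45/53 vs 23/25 | −7.1 |
| 3 / 0 | 45/50 vs 23/25 | −2.0 |
| 1 / 1 | 45/52 vs 23/24 | −9.3 |
| 3 / 1 | 45/50 vs 23/24 | −5.8 |

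With 25 in the control arm, one exclusion moves its rate by 3.8 points (92.0% to 95.8%), so the sign of the shift is open.

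**6. Leverage on the interval.** Hypothetical 45/50 vs 23/25, using the SAP 6.1.2 standard error without strata (stratum counts are not given): difference −2.0 points, lower 95% limit −16.6. With three LEN failures dropped and none from control, 45/47 vs 23/25: difference +3.7, lower limit −9.7. This is a one-sided case chosen to show sensitivity, not an estimate.

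**The case against.** The strongest reply is that little depends on this analysis. The primary analysis is on the FAS. SAP 6.3.1 adds Missing = Failure on the FAS, which is stricter. SAP 3.1 requires counts by set and a by-subject listing of reasons for exclusion, SAP Appendix 3 item 14 flags these very participants, and exclusions are settled before database lock. The trial is described as non-confirmatory. Route (c) can also include people lost before suppression was possible, whom some would call non-evaluable. All of this limits the harm. None of it corrects the PP estimate, and fixing the list before lock does not help when the rule itself depends on the outcome.

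Four stronger readings are tempting, and the documents do not support them:

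- *Every snapshot failure without the ticked box is dropped.* Those viraemic on treatment in the window stay in under this criterion.
- *The 11 of 17 subcutaneous stops recorded as participant decision, loss to follow-up or investigator's discretion measure the problem.* Those with last RNA < 50 belong to the no-data category, which a PP set ordinarily excludes. The count also runs to the data cut: with 17 stops and only 13 non-successes, at least 17 − 13 = 4 of the stopped participants were Week 54 successes.
- *The losses fall mainly in Groups 1 and 2 through miscoding.* Lack of efficacy is a listed reason and was used for 3 subcutaneous participants. Protocol 6.7 is redacted and the eCRF guidance is not available, so coding practice cannot be judged.
- *The comparison is biased toward LEN.* Step 5 shows that the difference can move either way.

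**Conclusion.** SAP 3.1.3 and 6.1.1 are inconsistent for one group: no window data, stopped for a reason other than AE, death or lack of efficacy, last on-treatment value ≥ 50. The first PP criterion, taken alone, raises or leaves unchanged each group's success rate. Other PP criteria, such as the adherence cut-off, may remove responders or failures, so the net PP result is not determined by this one alone.

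The number affected is not reported. About 1 percentage point per participant in the pooled subcutaneous groups rests on the assumptions in step 3; the limit of 6 of 105 rule-stopped cases assumes that such stops took effect by the end of the Week 28 window. No direction is established for the LEN minus B/F/TAF difference. The FAS primary result and Missing = Failure are untouched. This is worth correcting, but it does not threaten the primary conclusion.

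**What to change.** Reword the exception in SAP 3.1.3: exclude participants without on-treatment HIV-1 RNA in the Week 54 window, except those whom the snapshot classifies as HIV-1 RNA ≥ 50 copies/mL, whether through lack of efficacy or through another reason with a last on-treatment value ≥ 50. These stay in the PP set as failures. Add a table of PP exclusions by arm and snapshot category, so that readers can see how many failures and how many no-data cases each arm loses.

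The cost is one sentence and one table, since the snapshot already derives the category. The PP rate may be slightly lower, and some early drop-outs not yet suppressed will count as failures, as they already do in the primary analysis. The reworded set would still exclude the no-data category, so a PP rate above the FAS rate remains expected. Because the SAP is signed and Protocol 1.2.2.8 already reports Week 54 results, the change belongs in the CSR as a documented deviation, as SAP Section 1 provides, with both PP versions shown.

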Parameter	GS-6207 Alone 300 mg (N = 30)	GS-6207 300 mg + COBI (N = 29)	GS-6207 300 mg + DRV/COBI (N = 29)
C _{max} (ng/mL)	30.6 (74.4)	57.8 (53.6)	61.5 (43.4)
AUC _{last} (h*ng/mL)	10,400 (77.7)	16,100 (61.3)	14,200 (47.3)
AUC _{inf} (h*ng/mL)	10,700 (76.8)	22,700 (62.5)	19,500 (48.7)
T _{max} (hours)	8.00 (6.00, 48.0)	8.00 (6.00, 48.0)	6.00 (6.00, 8.00)
t _{1/2} (days)	12.3 (9.97, 15.9)	18.8 (15.9, 24.2)	16.8 (14.5, 19.3)

%CV = percentage coefficient of variation; COBI = cobicistat; DRV = darunavir; Q1 = first quartile; Q3 = third quartile
 Pharmacokinetic parameters are presented as Mean (%CV) except T_{max}, t_{1/2}, and T_{last}, which are presented as median (Q1, Q3), and shown to 3 significant digits

Cohort 4 served as a reference arm for Cohorts 8 and 10; in Cohort 4, participants received a single dose of GS-6207 300 mg tablet alone (N = 27). Participants in Cohort 8 received 25 days of RIF (600 mg QD), with GS-6207 administered on Day 14, and participants in Cohort 10 received a single dose of FAM (40 mg) 2 hours prior to a GS-6207 on Day 1 (N = 25 per cohort). All GS-6207 doses were administered in the morning under fasted conditions. Pharmacokinetic samples were obtained up to Day 23 post GS-6207 dose (Cohorts 4 and 10) and up to Day 12 post dose (Cohort 8) to characterize the PK of GS-6207 in each treatment. Safety data analysis is ongoing.

The median t_{1/2} of GS-6207 administered alone was 13.4 days (Table 1-6). Following co-administration with RIF, GS-6207 C_{max} and AUC_{inf} were approximately 2.5-fold and 5-fold lower, respectively, with a corresponding ~5-fold decrease in t_{1/2}. These data support the existing recommendations to disallow use of strong inducers with GS-6207.

Following co-administration with FAM, no change in GS-6207 exposure or t_{1/2} was observed; accordingly, use of famotidine and other acid reducing agents is permitted with GS-6207.

Table 1-6. GS-US-200-4333: Preliminary Plasma Pharmacokinetic Parameters of GS-6207 300 mg Tablet Following Administration Alone or with RIF (600 mg QD) or FAM (40 mg) [N = 25-27 per cohort]

Parameter	GS-6207 Alone 300 mg (N = 27)	GS-6207 300 mg +RIF (N = 25)	GS-6207 300 mg +FAM (N = 25)
C _{max} (ng/mL)	20.4 (102)	8.17 (59.6)	18.6 (60.2)
AUC _{last} (h*ng/mL)	3880 (65.3) ^a	745 (48.1) ^b	4610 (58.3)
AUC _{inf} (h*ng/mL)	5430 (58.0) ^a	786 (47.7) ^b	6360 (52.9)
%AUC _{exp}	30.0 (24.6) ^a	5.20 (50.7)	28.5 (24.7)

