4.2. Inclusion Criteria

Participants must meet all of the following inclusion criteria to be eligible for participation in this study:

- 1) Willing and able to provide written informed consent prior to performing study procedures
- 2) Aged ≥ 18 years
- 3) Antiretroviral naïve with no use of any ARV within one month of Screening. Use of pre-exposure prophylaxis (PrEP) (any duration), post-exposure prophylaxis (PEP) (any duration), or HIV-1 treatment (< 10 days therapy total) > 1 month prior to Screening is permitted
- 4) Plasma HIV-1 RNA ≥ 200 copies/mL at Screening
- 5) CD4+ cell count ≥ 200 cells/ μ L at Screening
- 6) A negative serum pregnancy test is required for all women at screening
- 7) Participants of childbearing potential who engage in heterosexual intercourse must agree to use protocol-specified method(s) of contraception as defined in [Appendix 4](#).
- 8) Lactating women must agree to discontinue nursing before the study drug(s) is administered

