4.3. Exclusion Criteria

Participants who meet *any* of the following exclusion criteria are not to be enrolled in this study:

- 1) An opportunistic illness requiring acute therapy within 30 days prior to screening
- 2) Active, serious infections (other than HIV-1 infection) requiring parenteral antibiotic or antifungal therapy within 30 days before screening
- 3) Active tuberculosis infection
- 4) Acute hepatitis within 30 days prior to screening

- 5) HBV infection, defined as screening results showing either or both of:
 - a) Positive HBV surface antigen
 - b) Positive HBV core antibody and negative HBV surface antibody
- 6) Hepatitis C virus (HCV) antibody positive and HCV RNA > lower limit of quantitation (LLOQ)
- 7) A history of or current clinical decompensated liver cirrhosis (eg, ascites, encephalopathy, or variceal bleeding)
- 8) Treatment within 3 months prior to screening, or anticipated treatment during the study period with immunosuppressant therapies, hydroxyurea, foscarnet, radiation, or cytotoxic chemotherapeutic agents without prior approval from sponsor prior to randomization. Agents disallowed in [Table 5-5](#) may not be considered for approval
- 9) Active malignancy requiring acute therapy (with the exception of local cutaneous Kaposi's sarcoma)
- 10) Current alcohol or substance use judged by the investigator to potentially interfere with the participant's study compliance
- 11) Clinically significant abnormal ECG at the screening visit
- 12) Any of the following laboratory values at screening
 - a) Estimated glomerular filtration rate (eGFR) ≤ 50 mL/min according to the Cockcroft-Gault formula for creatinine clearance {[Cockcroft 1976](#)}
 - b) Alanine aminotransferase (ALT) $> 5 \times$ upper limit of normal (ULN)
 - c) Direct bilirubin $> 1.5 \times$ ULN
 - d) Platelets $< 50,000/\text{mm}^3$
 - e) Hemoglobin < 8.0 g/dL
- 13) Participation or planned participation in any other clinical trial (including observational trials) without prior approval from the sponsor throughout the study
- 14) Prior use of, or exposure to, GS-6207
- 15) Known hypersensitivity to the study drug(s), the metabolites, or formulation excipient
- 16) Use or planned use of exclusionary medications, refer to [Section 5.4](#)
- 17) Any other clinical condition or prior therapy that, in the opinion of the investigator, would make the participant unsuitable for the study or unable to comply with dosing requirements

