Phosphodiesterase-5 Inhibitors		Sildenafil, Vardenafil, Tadalafil: It is recommended that a single dose of Sildenafil no more than 25 mg in 48 hours, Vardenafil no more than 2.5 mg in 72 hours, or Tadalafil no more than 10 mg in 72 hours be coadministered.
Sedatives/Hypnotics		Midazolam, Triazolam

Medication Class	Disallowed Medications	Use Discouraged and To Be Used With Caution
Systemic Corticosteroids	All agents, including dexamethasone	

For participants in Treatment Groups 1, 2, and 3, physicians should also refer to the most current package insert for F/TAF for guidance on concomitant medications while participants are receiving treatments containing TAF (TAF single agent or F/TAF).

For participants in Treatment Groups 2 and 4, physicians should also refer to the most current package insert for B/F/TAF for guidance on concomitant medications while the participants are receiving BIC.

Medications to treat disease conditions excluded from the protocol are not listed under this Concomitant Medication section and are disallowed in the study. Medications for malignancy are not included in the table.

Should participants have a need to initiate treatment with any disallowed concomitant medication, the medical monitor must be consulted prior to initiation of the new medication. In instances where disallowed medication is initiated prior to discussion with the sponsor, the investigator must notify Gilead as soon as they are aware of the use of the medication.

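### The Per-Protocol set misstates exclusion 8 and omits inclusion 3, exclusions 14 and 16 and on-treatment use of disallowed drugs, so it cannot show robustness to those violations

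*SAP*

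**What the plan says.** SAP 3.1.3 starts from the FAS and removes four kinds of participant:

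- those without on-treatment HIV-1 RNA in the Week 54 window, unless they stopped for lack of efficacy;
- "Subjects who meet the exclusion criterion that was known hypersensitivity to the study drug(s), the metabolites, or formulation excipient";
- those who meet the criterion on treatment before or during the study "with immunosuppressant therapies, hydroxyurea, foscarnet, radiation, or cytotoxic chemotherapeutic agents that listed in Table 5-3 in protocol Section 5.4";
- "subjects with adherence rate for active once daily study drug(s) up to the Week 54 Visit below the 2.5th percentile".

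Protocol 4.3, exclusion 8, is the source of the third bullet. It bars the same classes unless the sponsor has approved their use before randomization. It then adds that agents disallowed in the drug-interaction table "may not be considered for approval".

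Three other protocol criteria bear on this point. Inclusion 3 requires participants to be antiretroviral (ARV) naive, with "no use of any ARV within one month of Screening"; it permits earlier PrEP, PEP or fewer than 10 days of HIV treatment. Exclusion 14 covers prior GS-6207. Exclusion 16 covers "Use or planned use of exclusionary medications". None of the three appears in SAP 3.1.3.

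SAP 6.1.3 gives the PP analysis one purpose: to test the robustness of the primary analysis. Membership is to be settled before database lock.

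**The concern.** In exclusion 8 the table narrows what the sponsor may approve. In the SAP it narrows who is removed. A participant who received a barred class without approval then stays in the PP set unless the agent also appears in a table built for a different purpose, drug interactions with GS-6207.

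The other gap is one of selection. The violations most directly tied to HIV-1 RNA response are prior ARV treatment beyond what inclusion 3 permits, prior GS-6207, and disallowed inducers or non-study ARVs taken during treatment. A strong inducer could lower response. A non-study ARV could raise it, and the written snapshot categories in SAP 6.1.1 contain no rule for that case. Such a participant can count as a success in both the FAS and the PP set. If neither set removes these violations, comparing the two results says nothing about them.

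**Working it through.** The plan gives no figure for this point, so the check sets the passages side by side, with a little arithmetic for scale.

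**1. Which table is meant.** The SAP follows protocol amendment 3 (SAP Section 1), which is not supplied. In the current protocol, Table 5-3 in Section 5.4 is the oral bridging schedule. Two leftovers show what the reference used to mean: the text of Section 5.5 still calls the medication list Table 5-3, and exclusion 16 still points to Section 5.4 for exclusionary medications. The current successor is Table 5-5 in Section 5.5.

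**2. Overlap of exclusion 8 with the current Table 5-5.** The Disallowed column has six classes: anticonvulsants, antimycobacterials, non-study ARVs, ergots, herbal supplements and systemic corticosteroids.

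| Class in the SAP bullet | Match in Table 5-5 |
|---|---|
| Immunosuppressants | Systemic corticosteroids, if counted as immunosuppressant (general knowledge, not stated in the documents) |
| Hydroxyurea | None |
| Foscarnet | None |
| Radiation | None |
| Cytotoxic agents | None; Section 5.5 states: "Medications for malignancy are not included in the table" |

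The caution column adds no match (dabigatran, digoxin, statins, PDE-5 inhibitors, sedatives). So 1 of 6 disallowed classes can overlap, and 4 of the 5 barred classes have no match.

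**3. Two readings of the clause.** If the table reference qualifies the whole list, only corticosteroid users can be removed. If it qualifies only the last item, the first four classes are screened in full but the cytotoxic limb is empty. Neither reading reproduces exclusion 8.

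**4. Criteria absent from the PP definition.** It uses exclusions 8 and 15 (hypersensitivity), that is 2 of 17 exclusion criteria, and none of the 8 inclusion criteria. A violator of inclusion 3, exclusion 14 or exclusion 16, or an on-treatment user of a disallowed drug, leaves only if also caught by missing Week 54 RNA or low adherence. This holds under either reading in step 3.

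**5. Why inducers matter.** Protocol 1.2.2.4, Table 1-6, gives mean exposure to a single 300 mg tablet alone and with rifampin:

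- AUCinf: 5430 / 786 = 6.9-fold lower (the text says about 5-fold)
- AUClast: 3880 / 745 = 5.2-fold lower

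The protocol draws its own conclusion: "These data support the existing recommendations to disallow use of strong inducers with GS-6207".

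**6. Weight of one participant.** This uses the Week 54 FAS counts in Protocol 1.2.2.8, as illustration only because PP counts are not given.

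| Group | Observed | One non-responder dropped | Change |
|---|---|---|---|
| 1 | 47/52 = 90.4% | 47/51 = 92.2% | +1.8 points |
| 2 | 45/53 = 84.9% | 45/52 = 86.5% | +1.6 points |
| 3 | 44/52 = 84.6% | 44/51 = 86.3% | +1.7 points |
| 4 (control) | 23/25 = 92.0% | 23/24 = 95.8% | +3.8 points |

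Dropping one responder changes little: 46/51 = 90.2% in Group 1 (-0.2 points) and 22/24 = 91.7% in control (-0.3 points). For comparison, the GS-6207 groups lie 1.6, 7.1 and 7.4 points below control.

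**The case against.** The strongest objections, and what remains of each:

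- **The amendment 3 table is not available, and Section 5.5 calls the current list representative rather than exhaustive.** This stands as a limit. A reader might infer that the third bullet can never remove anyone; the documents do not support that, because corticosteroids remain and the cited version is unseen. Nor is the outdated table number a SAP error in itself; it follows from the protocol version used.
- **The clause may be a careless carry-over, with exclusion 8 meant in full.** Possible. The remedy is then the same deletion, and the absent criteria are unaffected.
- **No passage says which violations must define a PP set.** True, and many unused criteria (consent, pregnancy, ECG) have no bearing on RNA response. The count in step 4 is descriptive. The point is confined to the criteria linked to response.
- **Violations are visible elsewhere.** SAP 4.3 tabulates eligibility failures and important deviations, SAP 7.4.1 and Appendix 3 list and flag non-study ARVs, and SAP 7.4.2 summarises other drugs. This helps a reader find such cases but does not make the PP analysis test their effect.
- **The consequence is small.** Largely accepted. The FAS is primary, SAP 3.5 calls the trial non-confirmatory, and no decision rule uses the PP result. The rifampin ratios come from single oral doses in healthy volunteers, not from the SC regimen, and active tuberculosis is already excluded.
- **A blanket ban on disallowed drugs up to Week 54 would bias the set.** This is correct and shapes the fix. The Disallowed column includes any non-study ARV, and Protocol 1.10 advises participants who leave the study to start other HIV therapy. Such a rule would delete failures who switched, whom the first PP bullet deliberately keeps. Protocol 1.2.2.8 reports three lack-of-efficacy discontinuations, all in the SC groups, so the deletion would favour GS-6207.

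**Conclusion.** The point holds in a limited form and should be corrected. The third PP bullet does not reproduce exclusion 8 under either reading of its wording. Judged by the current Table 5-5, the overlap is at most systemic corticosteroids and is empty for hydroxyurea, foscarnet, radiation and cytotoxic agents. Independently of that, no PP bullet removes violators of inclusion 3, exclusion 14 or exclusion 16, or users of disallowed drugs while on study drug. FAS-PP agreement therefore cannot be cited as robustness to those violations.

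Two stronger readings are not supported. A reader might infer that the Week 54 result is distorted: the documents give no count of such participants, and it may be zero. A reader might also infer that anyone with past ARV use is wrongly kept: inclusion 3 permits the PrEP, PEP and short treatment described above, so only use beyond that is at issue.

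The conclusion assumes that Table 5-5 succeeds the table the SAP cites and that corticosteroids count as immunosuppressants. If they do not, the overlap on the wider reading is empty.

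**What to change.** In SAP 3.1.3:

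1. Delete the closing clause of the third bullet that refers to Table 5-3 and Section 5.4, so that it matches exclusion 8: any listed class used without sponsor approval.
2. Add PP exclusions for violation of inclusion 3, exclusion 14 or exclusion 16.
3. Add a PP exclusion for use of any agent in the Disallowed column of the drug-interaction table, cited by title, from Day 1 to the earlier of the last dose date (SAP 3.8.1) and the Week 54 assessment.
4. For the B/F/TAF group, apply the medication rule through the interaction guidance that Protocol 5.5 names for that group, the B/F/TAF package insert, because the table is specific to GS-6207.
5. State that ARVs started after study drug discontinuation do not trigger exclusion, and that lack-of-efficacy discontinuations stay in the PP set as failures, as the first bullet provides.

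Because Week 54 results already appear in Protocol 1.2.2.8, any revised Week 54 PP analysis should be labelled post hoc and documented in the clinical study report, as SAP Section 1 requires for changes after finalization.

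The cost is SAP wording and a review of eligibility deviations and medications already collected. The PP set may be slightly smaller and its interval slightly wider.
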